#### B. Hypotheses / Research Question(s)

Overgrowing opportunistic pathogens in gut microbiome may be one of the major driver for developing more severe complications in patients who have COVID-19. Our overall hypothesis is that supplementing COVID-19 patients with a combination of fermentable dietary fibers of diverse physicochemical structures provides an additional energy source that will promote a select group of acetate and butyrate producers in the gut. Akin to the tall trees as the foundation species for a closed forest, this group of bacteria may work as the "Foundation Guild" in the gut microbiota that change the gut environment and suppress the overgrowing opportunistic pathogens, which may reduce the severity of COVID-19-related illness.

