## D. Endpoints

- 1. Primary outcome:
  - Gut microbiota composition
- 2. Secondary outcomes:
  - At Days 1, 14, 28 and 56:
  - a) Outcome of COVID-19-like illness (hospitalization or death)
  - b) Proportion of participants who are "alive and not admitted to the hospital"
  - c) Proportion of participants who visit the emergency room
  - d) Proportion of participants who have complete resolution of all objective symptoms, i.e. all vital signs are within the normal range for at least 48 h, including body temperature (oral) 36.5-37.5°C (97.7-99.5°F), pulse rate 60-100/min, respiratory rate 12-20/min and oxygen saturation level at 95-100%
  - e) Proportion of participants who have complete resolution of subjective symptoms, i.e. absence of all COVID-19-like symptoms listed by CDC (updated May 13, 2020) for at least 48 h, including the presence of chills or "feeling feverish", cough, shortness of breath or difficulty breathing, fatigue, muscle or body aches, headache, new loss of taste or smell, sore throat, congestion or runny nose, nausea or vomiting and diarrhea
  - f) Proportion of participants who have complete resolution of subjective symptoms except fatigue and cough, i.e. absence of all COVID-19-like symptoms listed by CDC (updated May 13, 2020) for at least 48 h, including the presence of chills or "feeling feverish", cough, shortness of breath or difficulty breathing, fatigue, muscle or body aches, headache, new loss of taste or smell, sore throat, congestion or runny nose, nausea or vomiting and diarrhea
  - g) Illness severity based on the categorization from FDA [18] and the Ordinal Scale for Clinical Improvement from the World Health Organization [19]
  - h) Body temperature (oral)
  - i) Oxygen saturation level
  - i) Pulse rate
  - k) Respiratory rate
  - I) Fasting blood glucose
  - Time to complete resolution of all objective symptoms
  - Time to complete resolution of all subjective symptoms
  - Time to complete resolution of all subjective symptoms except fatigue and cough

Protocol Title: COVGUT20

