## 1.5 Sample Size Justification

We will enroll a total of 100 participants who have COVID-19-like symptoms and have positive/pending PCR-based COVID-19 test results. These individuals will be randomized into the control and treatment group in a 1:1 ratio (i.e. 50 participants/group). With the assumption of a positivity rate of 40-50% in symptomatic participants in the USF Carol & Frank Morsani Center for Advanced Healthcare drive-through testing center, we expect to have at least 20 confirmed COVID-19 cases in each group. We used the micropower R-package [27], in which the weighted Jaccard distance matrix was simulated based on within-group distance variance (mean and standard deviation) of data from 36 T2DM patients (unpublished data) to estimate the required sample size. Using the simulated matrices, the PERMANOVA powers are calculated for varying effect sizes ( $\omega^2$ ) and sample sizes. Our results show that 16 subjects per group afford 80% power to an  $\omega^2$  of 0.0106 which correspond to the difference ( $\omega^2$ =0.0120) between the control and treatment group with a similar high-fiber intervention in the T2DM patients (unpublished data). We therefore aim to recruit 20 confirmed COVID-19 cases in each group to allow for potential dropouts and/or incomplete sample/data sets from the participants.

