# E. Minimizing Risks of Harm

Participants will be provided with oral and written instructions and supplies to collect fecal samples at home without direct physical contact with the specimens throughout the process. The specimens will be stored in a sealed container, a leak-proof secondary package (a sealable plastic bag lined with absorbent pads) and an outer package (e.g. a shipping box). Participants are not required to store the samples at home; they will mail the specimens to the research team using the shipping supplies provided.

To minimize adverse effects due to NBT-NM108, participants in the treatment group will be asked to gradually increase the dose to avoid adverse events associated with an acute increase in fiber intake. They will also be advised to drink enough fluids throughout the study including the amount of water taken together with NBT-NM108) to avoid constipation. Participants will be asked to monitor potential adverse events daily. If participants report an adverse event, a member of the study team will contact them to ask follow-up questions about the degree of severity (mild, moderate, or severe) and the frequency of the adverse events. The study physician (co-PI [name]) will assess the adverse events and, if necessary, she will instruct the participants to reduce the consumption of NBT-NM108 to a lower dose that has been tolerated, and so on. If the same level of discomfort continues i.e.. for three consecutive days, the treatment will be discontinued. Participants are also at asked to closely monitor their blood glucose level and discuss with their family physicians about adjusting their medications to prevent hypoglycemia.

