#### 6.0 Data Management Plan

#### 6.1 Data Analysis

DNA, protein, and metabolites will be extracted from fecal samples. 16S rRNA gene V4 region sequencing and metagenomic shotgun sequencing with different platforms such as Ilumina and PacBio will be done using the extracted DNA. Metaproteome profiling will be achieved using mass spectrometry-based proteome analysis based on extracted protein. Metabolomics will be measured using fecal sample supernatant. Multiomics data will be combined with clinical data for statistical analysis to explore the overall changes during COVID-19 course and changes induced by the treatment.

16S rRNA gene sequencing data will be analyzed based on the amplicon sequence variants (ASVs) [28] to determine the gut microbiota composition using QIIME 2 [29]. Shannon index and ASV richness will be used to assess alpha diversity. Principal coordinate analysis will be used to compare and visualize dissimilarity in gut microbiota structure between samples based on beta diversity (Weighted and Unweighted UniFrac distance) and statistical differences will be tested using permutational multivariate analysis of variance (PERMANOVA). PICRUSt 2 will be used to predict the functions of individual ASVs and the collective functions of the gut microbiota at the gene content and pathway levels [30]. Global functional profiles of the gut microbiota will be compared and visualized by principal component analysis.

Metagenomic sequencing data will be analyzed in a genome-centric way. The raw sequencing data will be processed with KneadData (https://huttenhower.sph.harvard.edu/kneaddata) for quality control. High quality draft genomes will be de novo assembled from the high-quality sequencing data. The quality assessment, taxonomic assignment and functional annotation of the genomes will be conducted by using CheckM [31], GTDB-Tk [32] and Prokka [33] respectively. Principal coordinate analysis will be used to compare and visualize dissimilarity in gut microbiota structure between samples based on beta diversity and statistical differences will be tested using permutational multivariate analysis of variance (PERMANOVA).

Protocol Title: COVGUT20

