To analyze the clinical data, Aalen's additive survival model will be used to test whether the impact of covarites on the cumulative hazard is time-dependent [35]. If the covariates do not vary with time, cox proportional hazards model will be subsequently used to adjust for age, gender, race/ethnicity, baseline COVID-19 severity, and whether the participant has taken treatments that may reduce COVID-19 severity (vaccination and monoclonal antibody treatment) as covariates. Survival analysis Kaplan-Meyer curves and log-rank test will be used to estimate and compare the risk of death and the risk of recovery, as a function of time, in participants with COVID-19-like symptoms [36, 37]. To compare the time to hospitalization, the time to recovery, the time to complete resolution of subjective symptoms, and the time to complete resolution of objective symptoms between treatment groups, we will use competing risks survival analysis (treating death or self-reported illness severity at Days 1, 14, 28 and 56 as a competing risk) [36, 38], use survival analysis without competing risk, and explore joint survival analysis and Bayesian survival model [39]. Specifically, cumulative incidence functions will be estimated and tested using Gray's test [40]. The Fine-and-Gray subdistribution hazard regression analysis [38] will be used to further adjust for age, gender, race/ethnicity, baseline COVID-19 severity, and whether the participant has taken treatments that may reduce COVID-19 severity (vaccination and monoclonal antibody treatment) as covariates. Proportion of participants who are "alive and not admitted to the hospital", proportions of participants who visit the emergency room at Days 1, 14, 28 and 56, have complete resolution of objective symptoms, have complete resolution of subjective symptoms and have complete resolution of subjective symptoms except cough and fatigue at Days 1, 14, 28 and 56 will be compared between groups using separate logistic regression analysis at each time point. Time for participants to have complete resolution of objective symptoms, complete resolution of subjective symptoms and complete resolution of subjective symptoms except cough and fatigue will be compared between groups using competing risks survival analysis described previously, treating death or self-reported illness severity at Days 1, 14, 28 and 56 as a competing risk [36, 38]. To compare the longitudinally (repeatedly) measured illness severity based on the Ordinal Scale for Clinical Improvement from the World Health Organization, body temperature (oral), oxygen saturation level, pulse rate, respiratory rate and fasting blood glucose between treatment groups, accounting for the effect of death, reported adverse event, or other appropirate competing risk, we will compare the treatment effect using the method of joint survival and longitudinal data analysis [41, 42], where each of the clinical outcomes (e.g., illness severity, body temperature (oral), and oxygen saturation level, etc.) will be modeled using linear mixed models, and death, reported adverse event, or other appropirate competing risk will be modelled using Weibull proportional hazards model [43]. Age, gender, race/ethnicity, baseline COVID-19 severity, and whether the participant has taken treatments that may reduce COVID-19 severity (vaccination and monoclonal antibody treatment) will be controlled as covariates in these statistical analyses, where appropriate. Within-group changes of main outcomes between groups will be modeled as change from pre- to post-treatment using ANOVA and modeled as the post-treatment value as the change itself with the pretreatment value entered as covariate using ANCOVA [44]. Lastly, alternative statistical methods will be explored to quantify the underlying differences between groups with respect to a time-to-event end point, robust methods include calculating ratio/difference of t-Year Survival Rates, ratio/difference of percentiles of survival functions, and ratio/differenceof restricted mean survival times or restricted mean time lost [45]. Statistical analyses described above will be conducted for both intent-to-treat dataset and per-protocal dataset. For each test of an outcome, we define the statistical significance by p<0.05. The false discovery rate [46] will be applied for multiple testing, where appropriate. Sensitivity analysis using multiple imputation methods [47] will be performed to handle the missing data. Other

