STATISTICAL ANALYSIS PLAP

TUDY TITLE: MODULATION OF GUT MICROBIOTA WITH NBT-NM108 AS AN ARLY TREATMENT FOR SUSPECTED OR CONFIRMED COVID-19 ATIENTS HORT NAME: COVGUT20 ROTOCOL ID: NBTNM10810012020 ;LINCIALTRIALS.GOV ID: NCT04540406

his document is confidential. It contains proprietary information of Notitia Biotechnologie ny viewing or disclosure of such information that is not authorized in writing by the Spons trictly prohibited. Such information may be used solely for the purpose of reviewing or erforming this study

Study Analysis Plan

Sequencing Data Analysis

DNA, protein, and metabolites will be extracted from fecal samples. 16S rRNA gene V4 region sequencing and metagenomic shotgun sequencing with different platforms such as Ilumina and PacBio will be done using the extracted DNA. Metaproteome profiling will be achieved using mass spectrometry-based proteome analysis based on extracted protein. Metabolomics will be measured using fecal sample supernatant. Multi-omics data will be combined with clinical data for statistical analysis to explore the overall changes during COVID-19 course and changes induced by the treatment.

16S rRNA gene sequencing data will be analyzed based on the amplicon sequence variants (ASVs) [1] to determine the gut microbiota composition using QIIME 2 [2]. Shannon index and ASV richness will be used to assess alpha diversity. The principal coordinate analysis will be used to compare and visualize dissimilarity in gut microbiota structure between samples based on beta diversity (Weighted and Unweighted UniFrac distance). Statistical differences will be tested using permutational multivariate analysis of variance (PERMANOVA). PICRUSt 2 will be used to predict the functions of individual ASVs and the collective functions of the gut microbiota at the gene content and pathway levels [3]. Global functional profiles of the gut microbiota will be compared and visualized by principal component analysis.

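### The primary-outcome PERMANOVA has no step that separates a difference in spread from a shift in composition, which matters if the evaluable arms differ in both size and spread

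*Protocol*

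**What the plan says.** Protocol section 1.3 D lists one primary outcome, "Gut microbiota composition", without a metric, time point or contrast. For the 16S data, section 6.1 plans principal coordinate analysis on beta diversity, "Weighted and Unweighted UniFrac distance) and statistical differences will be tested using permutational multivariate analysis of variance (PERMANOVA". The SAP (Sequencing Data Analysis) repeats it: "Statistical differences will be tested using permutational multivariate analysis of variance (PERMANOVA". Both documents name PERMANOVA again for the metagenomic data. MaAsLin2 is also listed, but it relates individual features to metadata and is not a global test of composition.

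The significance rule is "For each test of an outcome, we define the statistical significance by p<0.05", with intent-to-treat and per-protocol datasets. Neither document gives a permutation scheme, a dispersion test, a statistic for unequal spread, or a rule for reading a significant PERMANOVA when the arms differ in spread.

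The hypothesis (section 1.1 B) concerns direction: the fibre mixture "provides an additional energy source that will promote a select group of acetate and butyrate producers in the gut". The sample size (section 1.5) rests on confirmed cases: "we expect to have at least 20 confirmed COVID-19 cases in each group".

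**The concern.** The scientific question is about location, that is, whether treated participants' communities move. The pseudo-F divides the between-group sum of squares by a pooled within-group variance, and free permutation generates the null that the two arms have the same distribution, spread included. When sizes and spreads both differ, the ratio is off even if the centres coincide.

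**Size.** Allocation is 1:1, but section 1.5 itself allows for dropouts and incomplete samples, and the per-protocol set can lose more from one arm. Any analysis of confirmed cases would have random counts per arm, because people with pending tests are randomized and test result is not a minimization factor.

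**Spread.** Only one arm takes the product. Section 4.7 E says "participants in the treatment group will be asked to gradually increase the dose", with individual reduction or discontinuation possible, which could widen that arm. Convergence on one bacterial guild could narrow it.

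Two misreadings are at stake. Greater variability in a smaller treated arm could be reported as a shift in composition. A real shift could be missed if the smaller arm is also the tighter one.

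**Working it through.** **1. The plan's own figure.** Section 1.5 states "Our results show that 16 subjects per group afford 80% power to an" omega-squared of 0.0106. The within-group distance mean and SD behind it are unpublished, so it cannot be reproduced exactly. What can be checked: 16/(1 - 0.20) = 20, and 50 x 0.40 = 20. From omega² = (F - 1)/((F - 1) + N) with N = 32, F - 1 = 32 x 0.0106/0.9894 = 0.343, so the expected pseudo-F is about 1.34. A Gaussian model with 155 equal, independent dimensions gives 84% power at 16 v 16, close to the stated 80%. That model is an assumption.

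**2. Why size and spread must both differ.** Let control have n1 and variance 1, and treated n2 and variance r, with no shift. The expected numerator is (n2 + n1·r)/N, and the expected pooled denominator is ((n1 - 1) + (n2 - 1)r)/(N - 2).
- 20 v 20, r = 2: 1.500/1.500 = 1.00
- 24 v 16, r = 1: 1.000/1.000 = 1.00
- 24 v 16, r = 1.5: 1.300/1.197 = 1.09
- 24 v 16, r = 2: 1.600/1.395 = 1.15
- 24 v 16, r = 0.5: 0.700/0.803 = 0.87

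This offset does not depend on dimension. Its effect on the test does, because the null SD of the pseudo-F is roughly √(2/d): about 0.11 for d = 155 and 0.45 for d = 10.

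**3. Rejection at 0.05 with no shift** (155 equal dimensions, 299 permutations, 1,500 runs; control listed first, r = treated/control variance):

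| Sizes | r | Pseudo-F | Welch-type |
|---|---|---|---|
| 20 v 20 | 1.5 | 5.0% | 5.0% |
| 22 v 18 | 1.5 | 9.2% | 4.5% |
| 22 v 18 | 2 | 16.1% | 5.7% |
| 24 v 16 | 1.25 | 11.4% | 5.5% |
| 24 v 16 | 1.5 | 17.7% | 5.4% |
| 24 v 16 | 2 | 33.0% | 4.5% |
| 24 v 16 | 0.5 | 0.1% | 5.7% |

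Repeat runs at 24 v 16 gave 16-18% (r = 1.5) and 31-33% (r = 2). Unequal sizes with equal spread gave 3-6%. With variances decaying as 1/k, so that a few dimensions dominate (not recalibrated to the stated power), 24 v 16 gave about 7-9% (r = 1.5) and 10-12% (r = 2).

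**4. Power at the section 1.5 effect, 24 v 16.** With equal spread, pseudo-F has 90.5% and Welch-type 90.4%. With the treated arm smaller and at half the variance, it is 61% v 94% if the average variance is held fixed, but 90% v 99% if the control variance is held fixed. The loss therefore depends on scaling.

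**5. How likely is imbalance?** For two independent Binomial(50, 0.4) counts of confirmed cases, P(|difference| ≥ 4) = 0.475 and P(|difference| ≥ 8) = 0.125; at 50% positivity they are 0.484 and 0.133. Averaging the 155-dimension rejection rate over these counts at 40% gives 6.4% (r = 1.5) and 8.7% (r = 2) for the pseudo-F, against 4.6% and 4.7% for the Welch-type statistic.

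**The case against.** Much of the opposing case stands.

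- A reader might infer that unequal group sizes alone invalidate the test. They do not; unequal spread is also needed, and the documents give no arm-specific spread.
- A reader might take 16-33% as the trial's error rate. Those cells need the treated arm to be smaller by 8 and also more variable; at 40% positivity it is smaller by 8 or more only 6.3% of the time.
- A confirmed-case subset is not a named analysis set. Section 6.1 names intent-to-treat and per-protocol; confirmed cases serve to size the trial. With 50 per arm and an assumed random 20% sample loss in each, the average rate was 5.6-5.7%.
- Some recruitment routes target people who have already tested positive. At an assumed 80% confirmed, P(|difference| ≥ 8) falls to 6.0%.
- Free permutation is the method's default, not text in the plan.
- If treatment does nothing, randomized arms share the same spread and the test is valid. Apart from selective loss, a dispersion difference is itself a treatment effect, so the issue is interpretation, in a trial whose stated purpose is feasibility and exploration.

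None of this supplies the missing step. If the spreads turn out to differ, the plan gives no rule for reading its primary p-value, and the rule would be chosen after the data are seen.

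**Conclusion.** The omission is real and affects the only primary outcome, but the claim is conditional. If the evaluable arms differ in both size and spread, a PERMANOVA p-value cannot be read as a shift in composition. With equal sizes, or with equal spread, the test holds near 5%. The documents do not support saying that the primary result will be wrong.

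The size depends on assumptions: variance ratios of 1.5-2, the 24 v 16 split, and a Euclidean Gaussian model rather than UniFrac. Under these, rejection without a shift is about 16-33% with 155 equal dimensions and about 7-12% when a few dimensions dominate. The average over chance imbalance, about 6-9%, is from the 155-dimension model with confirmed-case counts at 40% positivity. This is a worthwhile, inexpensive improvement, not a fatal flaw.

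**What to change.** In protocol section 6.1 and the SAP's Sequencing Data Analysis, for both the 16S and the metagenomic data:

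1. For the cross-sectional between-arm comparison at each post-baseline time point, use a Welch-type distance statistic: the between-group sum of squares divided by s1²/n1 + s2²/n2, with the same permutations. Use it in place of the pooled pseudo-F or, at minimum, beside it as a pre-specified check.
2. Report a test of multivariate dispersion between arms alongside.
3. State that a shift in composition is claimed only if the Welch-type test supports it, and that a dispersion difference is reported as its own result.

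The cost is a few sentences and a few lines of code on the same distance matrices. At equal sizes the permutation p-values are identical, and at equal spread no material power is lost.

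There are three downsides. A result driven by dispersion no longer counts as a shift. The statistic as written does not cover repeated samples or covariates. It also reduces sensitivity to dispersion without fully removing it: in a Dirichlet/Bray-Curtis check with equal mean composition and a squared-distance ratio of about 1.3, the pseudo-F rejected 18% or 7% of the time depending on which arm was smaller, and the Welch-type statistic 12.5% or 10.5%. That is why the dispersion test belongs beside it.

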## **B.** Data Points

- Gut microbiota composition: fecal samples will be collected at Days 0, 28, 56 and the day when participants recover from COVID-19-like illness (if before Day 56)
- Clinical progress of COVID-19-like illness: 1) objective and subjective symptoms data will be collected twice a day from Day 1 to Day 28 or until they recover from COVID-19-like illness (whichever is later) and once a week thereafter until Day 56 (i.e. in the mornings of Days 35, 42, 49 and 56); and 2) COVID-19-like illness severity will be assessed at Days 1, 14, 28 and 56 using the categorization from FDA [18] and the Ordinal Scale for Clinical Improvement from the World Health Organization [19]
- Proportion of participants who are "alive and not admitted to the hospital" at Days 1, 14, 28 and 56
- Proportion of participants who visit the emergency room at Days 1, 14, 28 and 56
- Outcome of COVID-19-like illness (hospitalization or death) at Days 1, 14, 28 and 56
- Glucose homeostasis if the participant has T2DM: fasting blood glucose will be measured in the mornings from Day 1 to Day 28 or until they recover from COVID-19-like illness (whichever is later) and weekly thereafter until Day 56

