
outcomes (e.g., illness severity, body temperature (oral), and oxygen saturation level, etc.) will be modeled using linear mixed models, and death, reported adverse event, or other appropirate competing risk will be modelled using Weibull proportional hazards model [16]. Age, gender, race/ethnicity, baseline COVID-19 severity, and whether the participant has taken treatments that may reduce COVID-19 severity (vaccination and monoclonal antibody treatment) will be controlled as covariates in these statistical analyses, where appropriate. Within-group changes of main outcomes between groups will be modeled as change from pre- to post-treatment usng ANOVA and modeled as the post-treatment value as the change itself with the pretreatment value entered as covariate using ANCOVA [17]. Lastly, alternative statistical methods will be explored to quantify the underlying differences between groups with respect to a time-to-event end point, robust methods include calculating ratio/difference of t-Year Survival Rates, ratio/difference of percentiles of survival functions, and ratio/differenceof restricted mean survival times or restricted mean time lost [18]. Statistical analyses described above will be conducted for both intentto-treat dataset and per-protocal dataset. For each test of an outcome, we define the statistical significance by p<0.05. The false discovery rate [19] will be applied for multiple testing, where appropriate. Sensitivity analysis using multiple imputation methods [20] will be performed to handle the missing data. Other approaches, such as methods of selection models [21] or use the pattern-mixture models such as the control-based pattern imputation approach, or the tipping-point approach [22, 23] will also be considered.

Reference

- 1. Callahan, B.J., et al., *DADA2: High-resolution sample inference from Illumina amplicon data.* Nat Methods, 2016. **13**(7): p. 581-3.
- 2. Bolyen, E., et al., QIIME 2: Reproducible, interactive, scalable, and extensible microbiome data science. 2018, PeerJ Preprints.
- 3. Douglas, G.M., et al., *PICRUSt2: An improved and extensible approach for metagenome inference.* bioRxiv, 2019: p. 672295.
- 4. Parks, D.H., et al., *CheckM: assessing the quality of microbial genomes recovered from isolates, single cells, and metagenomes.* Genome Res, 2015. **25**(7): p. 1043-55.
- 5. Chaumeil, P.A., et al., *GTDB-Tk: a toolkit to classify genomes with the Genome Taxonomy Database.* Bioinformatics, 2019.

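### The adjusted Cox model is made conditional on a time-constancy test in Aalen's additive model, which does not check proportional hazards, and no step is given if the test fails

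*Protocol*

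**What the plan says.** The protocol (6.1 Data Analysis) and the SAP (Clinical Data Analysis) carry the same rule. First, "Aalen's additive survival model will be used to test whether the impact of covarites on the cumulative hazard is time-dependent". Then, "If the covariates do not vary with time, cox proportional hazards model will be subsequently used", with adjustment for age, gender, race or ethnicity, baseline severity, and vaccination or antibody treatment. Age, gender, race and baseline severity are fixed at entry, so the condition must refer to covariate effects and not to the covariates themselves.

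No sentence opens the other branch. The documents also do not state the level of this test (the 0.05 level is set for tests of outcomes), whether one flagged term is enough, or any diagnostic for proportional hazards.

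The Cox model appears to serve the part of the plan that will "use survival analysis without competing risk". Kaplan-Meier curves with the log-rank test, Gray's test and covariate-adjusted Fine-Gray regression are planned without this condition. Later, "alternative statistical methods will be explored to quantify the underlying differences between groups with respect to a time-to-event end point"; the list includes "restricted mean survival times or restricted mean time lost" but is not linked to the result of the Aalen test.

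The outcomes concerned are secondary, for example "Time to complete resolution of all objective symptoms" (protocol 1.3 D). The primary outcome is gut microbiota composition.

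**The concern.** A gate in front of a Cox model is useful only if it tests what the Cox model assumes, namely a hazard ratio that is constant over time. The Aalen test asks whether the hazard difference is constant. These are different properties. The gate can therefore admit a Cox model whose hazard ratio drifts, and can exclude one whose hazards are exactly proportional.

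Because nothing is written for a failed test, the analysts would choose the next step after seeing the data. At stake is whether, and on what basis, an adjusted Cox hazard ratio is reported for recovery, symptom resolution, hospitalization and death.

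**Working it through.** The plan gives no figure for this rule to reproduce. The only power statement (protocol 1.5) concerns PERMANOVA. The check is therefore algebra, the documents' own outcome definitions, and simulation under assumed hazards.

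**1. Algebra (no assumptions).** For a binary treatment:

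- Constant additive effect: h1(t) = h0(t) + b, so HR(t) = 1 + b/h0(t).
- Constant hazard ratio r: h1(t) = r·h0(t), so the additive effect is (r − 1)·h0(t).

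Both are constant together only if h0(t) is flat or there is no effect.

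**2. Illustration, with assumed h0(t) = 0.002t per day.**

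| Day | h0(t) | HR if b = 0.02: 1 + 0.02/h0(t) | Additive effect if HR = 1.5: 0.5·h0(t) |
|---|---|---|---|
| 5 | 0.010 | 3.0 | 0.005 |
| 10 | 0.020 | 2.0 | 0.010 |
| 20 | 0.040 | 1.5 | 0.020 |
| 40 | 0.080 | 1.25 | 0.040 |

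The third column meets the condition but is not proportional. The fourth is proportional but does not meet the condition.

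**3. Could the baseline be flat?** Not for recovery. Protocol 1.3 A requires a minimum of ten days from symptom onset, so anyone enrolled sooner has zero hazard at first and a positive hazard later. For resolution, the definition requires that "all vital signs are within the normal range for at least 48 h" (the subjective outcomes carry the same 48-hour rule), while "objective and subjective symptoms data will be collected twice a day from Day 1 to Day 28". If resolution is dated at the end of the 48 hours, none can occur before about Day 3. The protocol does not say which end is used. A flat hazard after a shared delay remains possible for resolution if the test starts after the delay, but nothing in the plan supports assuming it.

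**4. Simulation.** Two arms 1:1, censoring at Day 56, treatment term only, level 0.05. The gate is a supremum test of a constant additive effect. The comparison is the scaled Schoenfeld test. There were 600 trials at N = 100 (the planned size) and 200 at N = 1000. All hazards and effects are assumptions.

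| Truth | N = 100: Aalen / Schoenfeld rejects | N = 1000: Aalen / Schoenfeld rejects |
|---|---|---|
| Proportional, HR 2, flat baseline | 3% / 5% | 4% / 2.5% |
| Proportional, HR 2, Weibull shape 2 | 11% / 6% | 92.5% / 5.5% |
| Proportional, HR 2, no event for 8 days, then flat | 24% / 6% | 100% / 7% |
| Additive 0.05/day, Weibull shape 2 | 5% / 37% | 6% / 100% |
| Additive 0.05/day, Weibull shape 3 | 6% / 72% | 10% / 100% |

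With a non-flat baseline the gate points the wrong way, clearly so at N = 1000. At N = 100 it mostly fails to object to anything.

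**5. Sensitivity to the assumed baseline.** Keep 50 per arm but set the hazard to zero before Day 3, followed by Weibull shape 1.5 or 2 or a lognormal (median parameter 14 days). The treatment gate then objects in 1.1–7.1% of exactly proportional trials (HR 1.75) and 1.8–5.1% of additive ones (0.05/day). It does not separate the two. Schoenfeld detection of the additive effect is 9–14% here, and 16–32% if the Weibull clock itself starts on Day 3, against 37–72% in the table.

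**The case against.** The strongest reply is that little depends on the gate. The outcomes are secondary, the stated aim is feasibility and exploration, and covariate-adjusted Fine-Gray regression, Gray's test and the log-rank test go ahead whatever the Aalen test shows. Restricted mean time is already listed. Neither document calls the Aalen test a proportionality check. All of this stands and limits the scope. It does not make the condition relevant to the Cox model or supply the missing branch. Aalen's model might be the intended fallback, but that is not written.

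The gate is also not blind to every departure. For an assumed effect that builds up (ratio 1 to Day 7, 2.5 from Day 14) it objects in 0.3–37% of trials, depending on the test horizon. The plan then gives no next step.

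Three stronger readings are tempting, and the documents do not support them.

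- *A reader might infer that about one trial in five would lose its adjusted Cox analysis.* Testing treatment and five covariates, with any flag counting as failure, gives 16–25% if the six tests are uncorrected. With a false discovery rate correction it is 0.2–4.4% (approximate, because only 300 resamples were used). The text states neither the any-flag rule nor whether its correction covers this test, so no such rate can be attributed to the plan.
- *A reader might infer that the Cox ratio would depend heavily on length of follow-up.* Follow-up is fixed at 56 days and no early Cox cut is planned. Under three assumed baselines the ratios at Day 28 and Day 56 were 1.79 and 1.76, 1.70 and 1.68, and 1.75 and 1.74.
- *A reader might infer false-positive inflation.* In null simulations the adjusted Cox test rejected in 5.4–6.2% of all trials and 5.6–5.9% of those passing the gate.

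**Conclusion.** The point holds in limited form. The condition is on the wrong scale, and no analysis is specified if it fails. This rests on the algebra and the text, not on simulation. For recovery, the protocol's own ten-day rule removes the flat-baseline case in which the two scales agree, provided that some participants enter within ten days of onset.

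It affects only whether, and with what apparent support, adjusted Cox hazard ratios are reported for secondary time-to-event outcomes. The primary outcome and the unconditional survival analyses are untouched. The practical size cannot be fixed from the documents, because they give no event-time distributions and the rejection rates move widely with the assumed baseline. The text should be corrected, but the point does not threaten the trial's main conclusion.

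**What to change.** In protocol 6.1 and the SAP, delete the Aalen condition and state:

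> The adjusted Cox model will be fitted for time to recovery and the time-to-resolution outcomes, whatever the result of the Aalen model. For death and hospitalization it will be fitted only if the number of events supports the covariates. Proportionality will be described with scaled Schoenfeld residuals or a treatment-by-time term and will not decide which model is reported. The difference in restricted mean time to Day 56 will be reported beside each Cox hazard ratio.

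Aalen's model may stay as an exploratory description. The limit for death and hospitalization is needed because events may be few among 100 home-isolated patients with mild to moderate illness; the documents give no rates. The Schoenfeld check stays descriptive because its detection rate at this size ranged from 9% to 72% across the assumed baselines.

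The cost is wording in two documents, no new data, and one more estimate per outcome by a method already listed. The restricted mean is not always the stronger analysis. In simulations at 50 per arm its power was 80–82% against 74–81% for Cox under an additive effect, 76–78% for both under proportional hazards, and 64–74% against 75–78% when the effect builds up late. It therefore belongs beside Cox, not in its place.
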